**Table 5: Primary Estimand Attribute for ORR**

| Estimand attribute  | Primary definition for study  |                     |
|---------------------------------|---|---------------------|
| Population                      | Subjects randomized into the study intended to include patients with radioiodine-refractory differentiated thyroid cancer who have progressed after prior VEGFR-targeted therapy. |                     |
| Endpoint                        | Radiographic response per RECIST 1.1  |                     |
| Intercurrent events             | Event   | Strategy            |
|                                 | Receipt of assigned study treatment   | Treatment policy    |
|                                 | Receipt of local radiation to bone  | Treatment policy    |
|                                 | Surgical resection of non-target tumor lesions  | Treatment policy    |
|                                 | Death   | Treatment policy    |
|                                 | Loss to radiographic follow up  | Treatment policy    |
|                                 | Receipt of local non-protocol anti-cancer medications other than for disease under study  | Treatment policy    |
|                                 | Surgical resection of target tumor lesions  | While on treatment* |
|                                 | Receipt of systemic non-protocol anti-cancer medications  | While on treatment* |
|                                 | Receipt of local non-protocol anti-cancer medications for disease under study   | While on treatment* |
|                                 | Receipt of local radiation to soft tissue for disease under study   | While on treatment* |
| Population summary              | Difference in proportions of subjects with a best overall response of confirmed complete response or confirmed partial response per RECIST 1.1 between treatment conditions.      |                     |
| Estimator                       | Fisher's exact test   |                     |

 See Appendix E for estimand terminology

\* A modified version of the “while on treatment” strategy is employed for these intercurrent events. Only data prior to the occurrence of these intercurrent events is of interest, but under the ITT principle, receipt of study treatment itself is not considered.

### 8.1.1.3 Hypothesis

The hypotheses to be evaluated in the analysis of the ORR are as follows:

$$H_0: ORR_{\text{Cabozantinib}} \leq ORR_{\text{Placebo}}$$

$$H_A: ORR_{\text{Cabozantinib}} > ORR_{\text{Placebo}}$$

where  $ORR_{\text{Cabozantinib}}$  and  $ORR_{\text{Placebo}}$  are the ORRs for the cabozantinib and placebo arms, respectively.

#### **8.1.1.4 Primary Analysis**

The primary analysis of ORR is based on tumor assessments per BIRC and will include all subjects in the OITT population.

Hypothesis testing for ORR will be performed using the Fisher's exact test at the 2-sided  $\alpha=0.01$  level of significance. If a sufficient number of responders are observed, analysis using the Cochran-Mantel-Haenszel (CMH) method to adjust for stratification factors per IRT may also be conducted.

Point estimates of ORR for each treatment arm, the difference in ORR between the two treatment arms, and associated confidence intervals will be provided. The odds ratio and its confidence intervals will also be shown. The 2-sided 95% and 99% CIs for the point estimate will be calculated using exact methods. The 2-sided 95% and 99% CIs for the difference in ORR between the two treatment arms and for the odds ratio will be calculated by asymptotic methods.

If the p-value for the two-sided Fisher's exact test is less than 0.01 and the point estimate for ORR in the cabozantinib arm is higher than that in the placebo arm, the null hypothesis of no difference in ORR will be rejected and it will be inferred that ORR is superior in the cabozantinib arm compared with the placebo arm.

The study will proceed to full enrollment of 300 subjects irrespective of the results of the ORR analysis in the OITT population.

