Approval of sorafenib is based on an international, randomized (1:1), placebo-controlled, Phase 3 study which enrolled 417 patients (207 sorafenib arm, 210 placebo arm) with RAI-refractory DTC (Brose et al, Lancet 2014). Patients received 400 mg sorafenib or matching placebo given orally twice-daily and were required to have measurable disease for eligibility. Prior receipt of targeted therapy or chemotherapy was not allowed. Median age was 63 years; male and female gender was equally represented. The majority of patients had ECOG PS of 0 or 1 (> 95%). The most frequent histologies were PTC (57%), FTC (25%), and poorly differentiated DTC (10%). The most common metastatic disease sites were lung (86%), lymph node (51%), and bone (27%). Sorafenib significantly improved the primary endpoint of PFS compared with placebo (median 11 vs 5.8 months; HR = 0.59; p-value < 0.0001) and also significantly improved ORR (12% vs 0.5%; p-value < 0.0001). An OS benefit was not observed in the ITT

population possibly due to crossover to active treatment after progression. The median duration of treatment was 10.6 months among patients who received sorafenib and 6.5 months among patients who received placebo. Dose reductions occurred in 64% of patients in the sorafenib group vs 9.1% in the placebo group, resulting in a mean sorafenib dose of 651 mg per day. Adverse events occurred in 98.6% of patients in the sorafenib group vs 87.6% in the placebo group. The most frequent AEs of Grade 3 or 4 in the sorafenib group versus placebo group were hand-foot skin reaction (20.3% vs 0%), hypertension (9.7% vs 2.4%), fatigue (5.8% vs 1.4%), diarrhea (5.8% vs 1%), and weight loss (5.8% vs 1%). Treatment discontinuation due to an AE occurred in 18.8% of sorafenib treated patients.

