Approval of lenvatinib is based on an international, randomized (2:1), double-blind, placebo-controlled, Phase 3 study which enrolled 392 patients (261 lenvatinib arm, 131 placebo arm) with RAI-refractory DTC (Schlumberger et al NEJM 2015). Patients received 24 mg lenvatinib or matching placebo once daily and were required to have measurable disease for eligibility. Up to one prior treatment regimen with a TKI was allowed. Median age was 63 years; males and females were equally represented. The majority of patients had Eastern Cooperative Oncology Group (ECOG) performance status (PS) of 0 or 1 (> 95%) and ~75% were treatment naïve and had not received a prior TKI therapy. The most common histology was PTC (~50%), followed by FTC (~19%), HTC (~18%), and poorly differentiated DTC (~13%). The most common metastatic disease sites were lung (~90%) and bone (~38%). Lenvatinib significantly improved the primary endpoint of progression-free survival (PFS) compared with placebo (median 18 vs 3.6 months; hazard ratio [HR] = 0.21; p-value < 0.001) and also significantly improved the objective response rate (ORR; 65% [4 complete responses {CRs} and 165 partial responses {PRs}] vs 1.5%; p-value < 0.001). There was no overall survival (OS) benefit in the intent-to-treat (ITT) population possibly due to post-progression crossover to active treatment. The median duration of treatment was 13.8 months among patients who received lenvatinib and 3.9 months among patients who received placebo. Dose reductions occurred in 67.8% in the lenvatinib group vs 4.6% in the placebo group, resulting in a mean lenvatinib dose of 17.2 mg per day. Treatment-related adverse events (AEs) occurred in 97.3% of patients in the lenvatinib group vs 59.5% in the placebo group. The most frequent AEs of Grade 3 or higher in the lenvatinib arm versus placebo arm were hypertension (41.8% vs 2.3%), proteinuria (10% vs 0%), decreased weight (9.6% vs 0%), fatigue or asthenia (9.2% vs 2.3%), diarrhea (8% vs 0%), and decreased appetite (5.4% vs 0%). Treatment discontinuation due to an AE occurred in 14.2% of lenvatinib treated patients.

Although initial therapy with VEGFR-targeting TKIs provides clinical benefits by improving PFS and ORR, the majority of DTC patients will acquire resistance to therapy and develop progressive disease (PD). For DTC patients who develop resistance to TKI therapy, options are very limited and more effective therapies are needed.

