#### **1.4.1.3 Phase 3 Study XL184-301**

A Phase 3, randomized, double-blind, placebo-controlled study (EXAM) was conducted in subjects with radiographically documented progression MTC. A total of 330 subjects were randomized in a 2:1 ratio to receive either cabozantinib (140 mg, capsule formulation) or placebo respectively. A significant increase in PFS per independent radiology review committee (primary endpoint) was seen in the cabozantinib arm compared with placebo (median of 11.2 vs 4.0 months; HR = 0.28; 95 CIs: 0.19, 0.40). For the secondary endpoint of ORR per independent radiology review committee, confirmed PRs occurred in 28% of cabozantinib-treated subjects and no placebo-treated subjects; responses were durable (median duration 14.6 months). The final analysis of the secondary endpoint of OS included 218 deaths and showed a non-significant trend for improved duration of OS in the cabozantinib arm compared with the placebo arm (medians of 26.6 vs 21.1 months, respectively; HR = 0.85; 95% CI: 0.64, 1.12; p = 0.2409). Because MTC is a relatively rare disease, the study was not designed to be large enough to provide high power to detect the minimum clinically significant difference in the secondary endpoint of OS.

In all subjects, the median duration of cabozantinib treatment was 10.8 months, and the 75th percentile for duration of treatment was 24.8 months. The maximum duration of treatment was 59.4 months at the data cutoff of the final OS analysis. A first dose reduction to 40 mg occurred in 82% of cabozantinib-treated subjects, and a second dose reduction to 20 mg occurred in 46% of cabozantinib-treated subjects. The safety population included a total of 214 subjects who received cabozantinib. The most frequent AEs ( $\geq 30\%$ ) were diarrhea (70.1%), weight decreased (57.9%), PPE (52.8%), decreased appetite (49.1%), nausea (46.7%), fatigue (42.5%), dysgeusia (35.0%), hair color changes (34.1%), and hypertension (32.7%). The most frequent Grade 3/4 AEs ( $\geq 5\%$ ) in cabozantinib-treated subjects were diarrhea (21.5%), PPE (12.6%), hypocalcemia (10.7%), lipase increased (10.7%), fatigue (9.8%), weight decreased (9.8%), hypertension (8.9%), decreased appetite (7.0%), asthenia (6.5%), hypokalemia (5.6%), and ALT increased (5.1%).

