## **9.2.2 Primary Analysis**

### **9.2.2.1 Objective Response Rate (ORR)**

The ORR is defined as the proportion of subjects with a best overall response of confirmed complete response (CR) or confirmed PR per RECIST 1.1. per BIRC, The primary analysis of ORR will be in the OITT population.

Hypothesis testing will be performed using the Fisher's exact test at the 2-sided  $\alpha=0.01$  level of significance.

Point estimates of ORR, the difference in ORR between the two treatment arms, and associated CIs will be provided. The 99% CIs will be calculated using exact methods except for the difference in ORR between the two treatment arms which will use asymptotic confidence limits.

If the p-value for the two-sided Fisher's exact test is less than 0.01 and the point estimate for ORR in the cabozantinib arm is higher than that in the placebo arm, the null hypothesis of no difference in ORR will be rejected and it will be inferred that ORR is superior in the cabozantinib arm compared with the placebo arm.

If sufficient responses are observed, additional supportive analyses will be conducted using appropriate methods to adjust for stratification factors.

The study will proceed to full enrollment of 300 subjects irrespective of the results of the ORR analysis in the OITT population.

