## 2.4 Power and Sample Size Justification

The study is designed to provide adequate power for both co-primary endpoints of ORR and PFS. It is estimated that 100 subjects would be adequate to evaluate the co-primary endpoint of ORR alone, and 300 subjects will be needed to evaluate the co-primary endpoint of PFS. Thus, to allow an earlier evaluation of ORR, this study employs a “trial within a trial design” (Hessel et al 2016). The primary analysis of ORR will be limited to the first 100 subjects randomized to the study and defined as the OITT population. Analysis of ORR is expected to occur 6 months after the last subject is enrolled in this population.

For ORR, 100 subjects provide a 2-sided 0.01 test of difference in proportions with > 90% power to reject the null hypothesis of no difference in ORR, assuming a true ORR of 2% in the placebo arm and 35% in the cabozantinib arm (a 33 percentage point difference), a pooled variance estimate, and a 2:1 allocation ratio.

For the primary endpoint of PFS, assuming exponential distribution, proportional hazards, and a 2:1 treatment allocation ratio (cabozantinib:placebo), 193 events are required to provide 90% power to detect an HR of 0.61 using the log-rank test and a 2-sided significance level of 0.04. This corresponds to a 36% reduction in the risk of progression or death, or a 64% improvement in median PFS from 5.5 months to 9.0 months. Under this design and with the application of the fallback method (see Section 8.2) the minimum observed effects that would result in statistical significance for PFS are:

- If Ho is rejected for ORR and PFS is tested at the 5% level under the fallback method, the minimum observed effect that would result in statistical significance for PFS is:

| Analysis | Information Fraction | p-value | HR    | Median PFS (months) |              |
|----------|----------------------|---------|-------|---------------------|--------------|
|          |                      |         |       | Placebo             | Cabozantinib |
| Interim  | 43%                  | 0.0013  | 0.474 | 5.5                 | 11.6         |
| Final    | 100%                 | 0.0496  | 0.742 | 5.5                 | 7.4          |

- If Ho is not rejected for ORR and PFS is tested at the original 4% allocation, the minimum observed effect that would result in statistical significance for PFS is:

| Analysis | Information Fraction | p-value | HR    | Median PFS (months) |              |

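### SAP 8.1.1.4 plans asymptotic intervals for the supplementary ORR odds ratio, although the design expects fewer than one placebo responder

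*Combined protocol and SAP*

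**What the plan says.** SAP 8.1.1.4 tests ORR in the OITT population (the first 100 subjects randomized 2:1) with Fisher's exact test at two-sided 1%. Success needs p below 0.01 and a higher cabozantinib rate. The per-arm rates get exact intervals. The section then adds an odds ratio: "The odds ratio and its confidence intervals will also be shown". The 95% and 99% "CIs for the difference in ORR between the two treatment arms and for the odds ratio will be calculated by asymptotic methods".

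Three other places bear on the point.

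- SAP Table 5 gives the population summary of the ORR estimand as "Difference in proportions of subjects with a best overall response of confirmed complete response or confirmed partial response" between treatment conditions. The odds ratio is therefore a supplementary measure.
- Protocol 9.2.2.1 plans no odds ratio. It makes the 99% intervals exact "except for the difference in ORR between the two treatment arms which will use asymptotic confidence limits".
- SAP 2.4 sizes the comparison "assuming a true ORR of 2% in the placebo arm and 35% in the cabozantinib arm".

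No section names the asymptotic method for the odds ratio or says what to do with an empty cell. The Clopper-Pearson default in SAP section 4 is for binomial variables and supplies no odds-ratio interval. The condition in 8.1.1.4 about having enough responders governs only the optional Cochran-Mantel-Haenszel analysis.

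**The concern.** Large-sample intervals for an odds ratio need reasonable counts in all four cells. This design expects one cell to hold 0 or 1. With no placebo responder the sample odds ratio is infinite and the usual log-scale standard error does not exist. With one placebo responder the log-scale interval exists but is very wide, and it can include 1 beside a Fisher test that rejects at 1%.

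What is at stake is presentation. The report could have no interval where one was planned, or a 99% interval that appears to contradict the positive test beside it. The handling would also be chosen after the data are seen, and the choice changes what is printed (see the 23/67 vs 0/33 example in the working).

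**Working it through.** **Inputs.** Response rates 35% and 2%, two-sided alpha 0.01, 100 subjects, 2:1 (SAP 2.4 and 3.2). The split of 67 cabozantinib to 33 placebo is derived from 2:1 and not stated; permuted blocks within strata could move it slightly, so 66:34 and 68:32 are shown too. The log-scale (Woolf) interval is assumed for the asymptotic method.

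**1. The plan's own figure.** SAP 2.4 states power above 90%.
- Pooled rate = (33 × 0.02 + 67 × 0.35)/100 = 0.2411.
- Null SE = √[0.2411 × 0.7589 × (1/33 + 1/67)] = 0.0910.
- Alternative SE = √[0.02 × 0.98/33 + 0.35 × 0.65/67] = 0.0632.
- Power = Φ[(0.33 − 2.576 × 0.0910)/0.0632] = 93.5%.

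Enumerating all 68 × 34 outcomes for Fisher's test gives 97.0%. The stated power holds.

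**2. Empty placebo cell.** Expected placebo responders = 33 × 0.02 = 0.66. P(none) = 0.98^33 = 51.3%; with 34 placebo subjects 50.3%, with 32 it is 52.4%. The other three cells are almost never empty. The Woolf standard error, √(1/a + 1/b + 1/c + 1/d), is then undefined at both confidence levels.

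Sensitivity to the placebo rate at n = 33: 71.8% at 1%, 36.6% at 3%, 18.4% at 5%. The protocol's background reports lower placebo rates: the sorafenib trial "also significantly improved ORR (12% vs 0.5%; p-value < 0.0001"), the lenvatinib trial "vs 1.5%; p-value < 0.001", and in the medullary thyroid cancer trial "confirmed PRs occurred in 28% of cabozantinib-treated subjects and no placebo-treated subjects". At 0.5% and 1.5% the chance is 84.8% and 60.7%.

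**3. Interval defined but including 1.** Take 20/67 vs 1/33, Fisher p = 0.0014.
- Odds ratio = (20 × 32)/(47 × 1) = 13.6; ln = 2.611.
- SE = √(1/20 + 1/47 + 1 + 1/32) = 1.050.
- 99%: exp(2.611 ± 2.576 × 1.050) = 0.91 to 204.
- 95%: exp(2.611 ± 1.960 × 1.050) = 1.74 to 107.

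With 1/33 on placebo, Fisher rejects from 16/67 but this 99% interval excludes 1 only from 22/67. Over all outcomes at the design rates, the 99% interval is defined and includes 1 despite rejection in 12.8% of trials (10.3% for 66:34, 13.9% for 68:32). The 95% interval, where defined, never does so.

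**4. How much the rule matters.** Take 23/67 vs 0/33, close to the design expectation, Fisher p = 0.00003.
- Woolf: not computable.
- Woolf with 0.5 added to each cell: 99% interval 0.85 to 1472.
- Likelihood-ratio: 99% lower limit 4.46, upper limit infinite.
- Exact conditional: the lower limit θ solves C(67,23)θ^23 / Σ C(67,k)C(33,23−k)θ^k = 0.005, which gives θ = 2.53; upper limit infinite.

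**5. The exact interval against the test.** Over all outcomes at the design rates, the exact conditional 99% interval includes 1 despite Fisher rejection in 1.3% of trials, and the 95% interval never does. For 20/67 vs 1/33 its 99% limits are 1.34 to 2941.

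**The case against.** The strongest objection is that the 51.3% belongs to an assumed method. The SAP says only asymptotic, and a likelihood-ratio interval fits that word and survives an empty cell. This stands: a reader might infer that the planned interval will be blank in about half of trials, but the documents support that only if the Woolf interval is meant. What remains without the assumption is that the method and the zero-cell handling are open.

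A second objection is that nothing inferential turns on the odds ratio. This also stands. A reader might infer that the ORR test, the alpha passed to PFS or the power is compromised. They are not: Fisher's p-value and the direction decide, no interval is used to judge success, and an interval built differently from the test will sometimes disagree with it.

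A reader might also extend the point to the difference interval. That interval can be computed with no placebo responder. A 99% Wald version covers 98.7% at the design rates and never includes 0 after rejection, though it excludes 0 without rejection in 2.4%. Replacing it is a trade-off that this problem does not require. Nor is there a figure to support a claim about the subgroup odds ratios, which SAP 8.5 plans only where applicable.

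The scope is narrow too. In the later descriptive ITT analysis, with about 100 placebo subjects, P(none) = 0.98^100 = 13.3%. The low background rates come from patients with no or mostly no prior TKI and from medullary cancer, so they illustrate an emptier cell without establishing one here.

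**Conclusion.** The point holds, as a minor one. SAP 8.1.1.4 commits to asymptotic odds-ratio intervals in a table where the design expects about 0.7 placebo responders, and leaves both method and zero-cell handling open. Under the log-scale reading at 35% vs 2% and 67:33, the interval is not computable in 51.3% of trials, and in a separate 12.8% the 99% interval includes 1 beside a positive 1% test. These figures rest on the Woolf assumption, the derived split and the design rates. The effect is confined to how a supplementary measure is reported in the 100-subject OITT analysis.

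**What to change.** In SAP 8.1.1.4, replace the asymptotic method for the odds ratio with the exact conditional interval at 95% and 99%. State that with no placebo responder it is reported as a lower limit with an infinite upper limit. Leave the difference interval as it is. Make the change by SAP revision or addendum before unblinding, as SAP 4.9 provides. Protocol 9.2.2.1 plans no odds ratio, so no protocol amendment is needed.

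The exact interval is preferable to adding 0.5 to each cell. At the design rates that correction covers only 92.6% and 97.5% for nominal 95% and 99%, and its 99% interval includes 1 despite rejection in 46.2% of trials.

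The cost is a wording change and an option in standard software. The exact interval is conservative, it still has no finite upper limit when the placebo cell is empty, and its 99% version still includes 1 despite rejection in about 1.3% of trials.

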#### **8.1.1.5 Sensitivity Analyses**

The analysis of ORR based on tumor assessments per RECIST 1.1 per investigator will also be analyzed following the same principles as outlined for the primary analysis described in Section 8.1.1.4. In addition, ORR will also be analyzed descriptively for the ITT population at the time of final PFS analysis.

The concordance in ORR assessment between BIRC and investigator will be summarized for the OITT population.

#### **8.1.2 Progression-Free Survival (PFS)**

The primary efficacy analysis for PFS will include all subjects in the ITT population.

##### **8.1.2.1 Definitions and Conventions**

For tumor assessment, CT or MRI of chest/abdomen/pelvis/neck (CAPN) will be performed at screening and every 8 weeks ( $\pm 7$  days) after randomization during the first 12 months on study. Upon subject completion of 12 months on study, these assessments will be performed every 12 weeks ( $\pm 14$  days).

The recorded date of radiographic progression is the date of the tumor assessment visit at which progression is declared. If multiple scan dates are associated with a tumor assessment visit, the earliest assessment date within the set will be chosen as the progression date.

Only adequate tumor assessments (ATAs) will be considered in the determination of radiographic progression and censoring dates. For the purpose of this study, an ATA is defined as one that results in a time point assignment of: response (complete or partial), stable disease/(non-CR, non-PD), or progression. For PFS, ATA is based on soft tissue evaluation by CT/MRI.

